Number of subjects	In this study, we predict that approximately 30% of patients will experience severe toxicity. A population of 250 eligible and evaluable patients will allow us to estimate this proportion with an accuracy of $\pm 5\%$, leading to a 95% confidence interval (24.3%; 35.7%). Subgroup analyses will also be carried out. Subgroups of patients will therefore be defined according to the TKI treatment received (pazopanib, regorafenib, sorafenib, etc.). Assuming that 50 patients are included in a subgroup with a toxicity rate of 30%, the resulting precision will be $\pm 12\%$, for a 95% confidence interval (17.3% ; 42, 7%).
---------------------------	--

STUDY FLOWCHART

		TREATMENT					Follow-up (Beyond 28 days after TKI discontinuation and up to 12 months after TKI initiation)
	SCREENING	Start of treatment D1	Month 1 (D28, ±2 days)	Month 2 (D56, ±2 days)	Month N	Discontinua tion of treatment (within 28 days)	
TKI	Information		MA				
Consultation	X	X	X				X
Eligibility criteria	X						
Informed consent	X						
Demographic data	X						
Height	X						
Weight	X			X			
History of the disease / Medical history / Previous treatments	X						
Performance status (ECOG)	X	X	X				
Biological assessment	X ¹						
Tumour evaluation	X ²		According to the centre's routine practice				
Geriatric evaluation	X ³			X ⁴		X ⁴	
Blood sample for pharmacogenomics		X					
Blood sample for pharmacokinetics			X				
Toxicities			X			X ⁵	
Concomitant treatments			X			X ⁵	
Vital status							X ⁶

1 Within 7 days before D1 of treatment initiation (same day possible): Haematology (CBC, platelets), Biochemistry (sodium, potassium, calcium, magnesium, phosphorus, glucose, LDH, urea, creatinine, ASAT, ALAT, Alkaline Ph., total bilirubin, albumin, total protein), Coagulation (INR, PT, aPTT), Thyroid function (free T4, TSH).

2 Within 4 weeks before D1 of treatment initiation (same day possible).

3 Within 7 days before D1 of treatment initiation (same day possible): G8, Charlson, Cardiovascular diseases, ADL, IADL, ECOG, Get Up and Go Test, verbal or visual fatigue scale, MNA.

4 Evaluation method during a consultation or telephone interview: % weight loss over the past few months, falls, verbal fatigue scale, ADL, IADL.

5 To be collected for 28 days after discontinuation of treatment.

6 Follow-up according to the centre's routine practice.

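### The stated precisions of ±5% (250 patients) and ±12% (subgroup of 50) disagree with the 95% intervals printed beside them, whose half-widths are 5.7 and 12.7 percentage points

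*Combined protocol and SAP*

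**What the plan says.** The Number of subjects entry of the protocol synopsis bases the sample size on the precision of a single proportion. Its premise is that "we predict that approximately 30% of patients will experience severe toxicity". For the whole cohort, planned at 250 evaluable patients, it says that the rate will be estimated "with an accuracy of $\pm 5\%$, leading to a 95% confidence interval (24.3%; 35.7"%.

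It then turns to subgroups defined by the tyrosine kinase inhibitor received. It takes one such subgroup as an example, "Assuming that 50 patients are included in a subgroup with a toxicity rate of 30"%, and concludes that "the resulting precision will be $\pm 12\%$, for a 95% confidence interval (17.3% ; 42, 7"%. The upper limit, printed with a stray space after a decimal comma, is 42.7%.

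The Data analysis method entry plans to report the severe toxicity rate as a frequency and percentage with a 95% confidence interval, overall and by drug. It does not name the interval method. Nothing in the document describes the two ± figures as approximate or truncated.

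**The concern.** Each sentence gives the same quantity twice, once as a ± figure and once as an interval, and the two do not agree. An interval of 30% ± 5 points would run from 25.0% to 35.0%, and 30% ± 12 points from 18.0% to 42.0%. The printed intervals are wider in both cases.

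Precision is the only sample-size justification in the available text, and the ± figures are the summary a reader is likely to carry away. Both are more favourable than the design delivers. A reader who took ±5% as a design target could also conclude, wrongly, that 250 patients are too few.

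**Working it through.** **Inputs**, all from the Number of subjects entry: p = 0.30; n = 250 overall and n = 50 in the subgroup; two-sided 95% confidence, z = 1.96.

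**Step 1. Half-widths of the printed intervals**
- n = 250: (35.7 − 24.3)/2 = 5.7 points, against a label of 5.
- n = 50: (42.7 − 17.3)/2 = 12.7 points, against a label of 12.

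**Step 2. Reproduce the intervals.** The normal-approximation half-width is z·√(p(1 − p)/n), with p(1 − p) = 0.21.
- n = 250: 1.96 × √(0.21/250) = 1.96 × 0.02898 = 0.0568, giving 24.3% to 35.7%.
- n = 50: 1.96 × √(0.21/50) = 1.96 × 0.06481 = 0.1270, giving 17.3% to 42.7%.

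All four printed limits are reproduced to one decimal. The rate, the sample sizes, the confidence level and the intervals therefore agree with one another, and only the labels do not fit.

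**Step 3. Size of the discrepancy**
- n = 250: 5.68 − 5 = 0.68 point.
- n = 50: 12.70 − 12 = 0.70 point.

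**Step 4. Can anything else explain the labels?**

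*Rounding.* To whole points, 5.68 and 12.70 become 6 and 13.

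*Confidence level.* For ±5 points, 0.05/0.02898 = 1.725, a level of about 91.6%. For ±12 points, 0.12/0.06481 = 1.852, about 93.6%. The text says 95% for both. A 90% level would give 4.77 and 10.66 points.

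*Interval method*, at 95%:

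| Method | n = 250: interval (half-width) | n = 50: interval (half-width) |
|---|---|---|
| Printed in the plan | 24.3% to 35.7% (5.7) | 17.3% to 42.7% (12.7) |
| Normal approximation | 24.3% to 35.7% (5.68) | 17.3% to 42.7% (12.70) |
| Wilson | 24.7% to 35.9% (5.65) | 19.1% to 43.8% (12.32) |
| Exact (Clopper-Pearson) | 24.4% to 36.1% (5.85) | 17.9% to 44.6% (13.37) |

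No method gives 5 at n = 250. At n = 50 the Wilson half-width rounds to 12, but its limits are not the printed ones.

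**Step 5. What the labels would require if they were targets.** n = z²·p(1 − p)/w², rounded up:
- w = 0.05: 3.8416 × 0.21/0.0025 = 322.7, so 323 patients rather than 250.
- w = 0.12: 3.8416 × 0.21/0.0144 = 56.02, so 57 patients rather than 50.

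**The case against.** The strongest reply is that nothing depends on these labels. The correct interval stands beside each one, the planned reporting uses 95% intervals and not the ± figures, and no test, threshold or stopping rule in the available text refers to them. That is true, and it is why the point is minor.

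A second reply is that the labels are simply truncated: 5.7 and 12.7 cut to their integer parts, one careless shortening made twice rather than two miscalculations. This is the likeliest origin. It explains the error without removing it, because a truncated half-width still claims more precision than the design gives.

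Third, the ±12% label taken alone is compatible with other standard 95% methods, since the Wilson half-width of 12.32 rounds to 12. That is correct for the subgroup only. The plan prints the normal-approximation limits there, and no such reading rescues ±5%.

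Finally, the plan does not say outright whether ±5% was a target or a description of the result, and as a target it would call for 323 patients. However, the intervals are computed from 250 and 50 and presented as the consequence of those sizes, so a labelling error is much the more natural reading. The damaged decimal in 42.7% raises the possibility that decimals were also lost from the labels in translation or text extraction, but nothing shows that this happened.

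**Conclusion.** The concern holds. At a 30% rate and 95% confidence, the precision is ±5.7 percentage points with 250 patients and ±12.7 with 50, where the plan states ±5% and ±12%. Precision is overstated by 0.68 and 0.70 point respectively. The conclusion rests only on the plan's own rate, sample sizes, confidence level and printed limits; the first step of the check needs nothing but the limits.

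This is a minor reporting error. It is not evidence that the sample size is wrong, and the intervals and planned analyses are not in question.

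**What to change.** In the Number of subjects entry, replace ±5% with ±5.7 percentage points and ±12% with ±12.7 percentage points. Writing percentage points also makes clear that the precision is absolute and not relative to the 30% rate. Leave both intervals, the planned 250 patients and the analyses unchanged.

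The cost is two corrected figures in one paragraph and a stated precision that is slightly less favourable. Enrolment and analysis are unaffected.

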Method of observation	
This is a non-interventional, multi-centre, prospective research study with collection of biological samples, in which 250 elderly cancer patients should be included for 24 months at several centres. Once the patient has signed the informed consent, the investigator will collect clinical data before the start of treatment. The investigator or the geriatric nurse will carry out a geriatric evaluation and take an initial blood sample to perform pharmacogenomic analyses. During treatment, the investigator will collect data concerning the type of treatment, toxicities and tumour response. A second blood sample will be taken at the end of the first month of treatment in order to perform pharmacokinetic analyses. A geriatric evaluation will be carried out after 2 months of treatment, either during a telephone interview or in consultation, in order to assess any toxic effects on the patient's general condition.
 
Once treatment has been stopped, patient follow-up data will be collected along with a final geriatric evaluation.

Information collected	The investigator sends to the Institut Bergonié coordinating clinical research assistant (CRA) the inclusion form including the number of the centre, the name of the principal investigator, the first letter of the patient's last name and the first letter of their first name, their age on inclusion, the eligibility criteria, identification of the treatment with TKI, the date of signature of the consent form, along with the date scheduled for the start of treatment. Each patient's personal data will be confidential (data protection act of 6 January 1978 amended by the act of 6 August 2004). On the case report form or any other study document, patients will be identified by their initials (first letter of last name and first letter of first name) and an inclusion number. The investigators should, however, keep a patient identification list in their binder.

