Data analysis method	
Primary endpoints: prediction of severe toxicity (defined as the occurrence of adverse events attributable to treatment resulting in either discontinuation of more than three weeks of treatment, permanent discontinuation of treatment, hospitalisation, death, disability or significant or lasting incapacity) of TKIs prescribed in the context of the Marketing Authorisation in patients aged 70 years or over with cancer.
 
Secondary endpoints: description of toxicities, non-progression rate at 6 months and progression-free survival at one year.
 
Analysis of toxicity: The severe toxicity rate, along with the incidence rates for toxicities grades 1-4 will be reported according to the eligible and evaluable population. These endpoints will be described using frequency, percentage and 95% confidence interval. The toxicity rate will also be reported by subgroup of patients according to the TKI. Prognostic factors of severe toxicity will be evaluated using logistic regression analyses.
 
Non-progression analysis: The non-progression rate at 6 months will be reported according to the eligible and evaluable population, but also by subgroup of patients according to the TKI used. This endpoint will be described using frequency, percentage and 95% confidence interval. Prognostic factors (clinical and geriatric) of 6-month non-progression rates will be evaluated using logistic regression analyses.
 
Analysis of PFS: PFS will be analysed using the Kaplan-Meier method. Median survival will be presented with a 95% confidence interval. Median follow-up will be calculated using the reverse Kaplan-Meier method. Multivariate analyses will be performed according to the Cox proportional hazards model after verifying the risk proportionality assumption.
 
Intermediate statistical analysis: After the inclusion of the first 150 patients, an intermediate statistical analysis will be performed.

Institut Bergonié
Pre-ToxE Protocol

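### The 95% interval for severe toxicity assumes independent patients and the plan makes no use of centre; if outcomes cluster by centre, the interval is too narrow

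*Combined protocol and SAP*

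**What the plan says.** The Method of observation section describes a non-interventional, multi-centre cohort in which "250 elderly cancer patients should be included for 24 months at several centres". The number and size of the centres are not given.

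The Number of subjects section says "we predict that approximately 30% of patients will experience severe toxicity" and derives the precision from that rate and the sample size alone, "leading to a 95% confidence interval (24.3%; 35.7"%). A second calculation covers treatment subgroups: "Assuming that 50 patients are included in a subgroup with a toxicity rate of 30"%, with an interval of 17.3% to 42.7%.

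The Data analysis method section defines the endpoint as treatment-attributable events leading to "discontinuation of more than three weeks of treatment, permanent discontinuation of treatment, hospitalisation, death, disability or significant or lasting incapacity". On the rates it says: "These endpoints will be described using frequency, percentage and 95% confidence interval". On predictors it says: "Prognostic factors of severe toxicity will be evaluated using logistic regression analyses". The combined document mentions no centre term, intraclass correlation, design effect, random effect or robust variance. The centre number is on the inclusion form (Information collected) and on the sample tubes (Collection of blood samples).

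**The concern.** A binomial interval is valid when patients' outcomes are independent. Here there is reason to doubt that. The study observes routine care, and the combined document sets no common rule for interrupting or stopping treatment, for admission to hospital, or for judging that an event is due to treatment. If centres differ in these habits, two patients from the same centre are more alike than two from different centres, and 250 patients carry less information than 250 independent ones.

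Two results could be affected. The first is the interval for the overall severe-toxicity rate, which would cover the true rate less often than 95%. The second is the search for prognostic factors. A factor that follows centre habit could look prognostic because of the centre and not the patient. Candidates are the TKI used, whether the investigator or the geriatric nurse makes the assessment, and whether fatigue is rated on a verbal or a visual scale. The documents do not say that any of these differs by centre, but they leave room for it.

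**Working it through.** **1. Inputs.** From Number of subjects: p = 0.30, n = 250, 95% confidence, and n = 50 for a subgroup. From Method of observation: several centres, number not stated. Assumed, because the documents do not give them: the number of centres k, equal sizes m = 250/k, and the intraclass correlation (ICC) on the probability scale.

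**2. The plan's own figures.** Half-width = 1.96 × √(0.30 × 0.70 / 250) = 0.0568, so 30% ± 5.68 points = 24.3% to 35.7%. With n = 50: 1.96 × √(0.21/50) = 0.127, so 17.3% to 42.7%. Both match the printed intervals. Wilson (24.7% to 35.9%) and Clopper-Pearson (24.4% to 36.1%) limits for n = 250 do not. The plan's interval is therefore the Wald interval with a design effect of 1.

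**3. Allowing for centre.** Design effect DE = 1 + (m − 1) × ICC. Half-width = 5.68 × √DE. Effective sample size = 250/DE. Approximate coverage of the interval computed as planned = 2Φ(1.96/√DE) − 1.

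| Centres (m) | ICC | DE | Half-width (points) | Effective n | Coverage |
|---|---|---|---|---|---|
| any | 0 | 1.00 | 5.7 | 250 | 95% |
| 20 (12.5) | 0.01 | 1.115 | 6.0 | 224 | 94% |
| 20 (12.5) | 0.02 | 1.23 | 6.3 | 203 | 92% |
| 20 (12.5) | 0.05 | 1.575 | 7.1 | 159 | 88% |
| 10 (25) | 0.01 | 1.24 | 6.3 | 202 | 92% |
| 10 (25) | 0.02 | 1.48 | 6.9 | 169 | 89% |
| 10 (25) | 0.05 | 2.20 | 8.4 | 114 | 81% |

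Example: 10 centres and ICC 0.05 give 5.68 × √2.20 = 8.4 points, or 21.6% to 38.4%.

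**4. What these ICCs mean.** The standard deviation of true centre rates around 30% is √(ICC × 0.21). That is 4.6 points at ICC 0.01 and 10.2 points at ICC 0.05.

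**5. Unequal centres.** With an assumed coefficient of variation of 0.6 in centre size, 10 centres and ICC 0.05, DE = 1 + (1.36 × 25 − 1) × 0.05 = 2.65, and the half-width is 5.68 × √2.65 = 9.2 points.

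**6. Prognostic factors.** Simulation of an ordinary logistic model with one null predictor, 10 centres of 25 patients, nominal 5% level. The ICC here is on the logit scale. At a 30% rate, 0.05 on that scale is about 0.034 on the probability scale, so these results should not be lined up with the ICC 0.05 rows above.

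- 10% of the predictor's variance between centres: type I error about 5% at logit-scale ICC 0.05 and about 6% at 0.10.
- 50% of the predictor's variance between centres: about 9% and about 13%.

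**The case against.** A reader might infer that the precision is overstated as a matter of fact. The documents do not support that. They give no ICC, number of centres or centre sizes, and every inflated figure above rests on assumptions. At ICC 0.01 with 20 centres the half-width moves only from 5.7 to 6.0 points, and at ICC 0 the printed interval stands.

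A reader might also infer that the endpoint consists of local care decisions. It does not. Death and disability or lasting incapacity are not care decisions, one definition applies at all centres, and treatment follows the Marketing Authorisation everywhere. The flowchart's references to each centre's routine practice concern tumour evaluation and follow-up, not toxicity. What remains is that interruption, stopping, admission and attribution can each be influenced locally.

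A third tempting reading is that the logistic models are affected as much as the rate. Most candidate predictors are patient-level (G8, ADL, IADL, MNA, comorbidities, pharmacokinetic and pharmacogenomic data) and should vary mainly within centres. For such factors, ignoring centre changes standard errors little, and sometimes in the opposite direction.

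Finally, the interval is a planning figure for a cohort, with no test or decision threshold tied to it. A mandatory random intercept would also be debatable: its variance is poorly estimated with few centres, its odds ratios are conditional on centre, and a prediction for a patient at a new centre cannot use an estimated centre effect. These arguments stand. They limit the size of the point and argue for a sensitivity analysis of the models, but they do not explain why a recorded centre variable is left unused.

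**Conclusion.** The point holds in conditional form, as a cheap improvement. It is certain that the printed interval assumes independence, that the cohort is multi-centre, and that the plan does not use centre. It is conditional that the interval for the overall rate is too narrow: this requires positive within-centre correlation, which is plausible for parts of the endpoint but not shown. With equal centres and ICCs of 0.01 to 0.05, the loss is modest with 20 centres (at most about 1.4 points of half-width, 7.1 − 5.7) and more noticeable with 10 (up to about 2.7 points, 8.4 − 5.7). Fewer or more unequal centres would make it larger.

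For prognostic factors, the effect is negligible when they vary mainly within centres. It deserves attention only for factors that differ strongly between centres.

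**What to change.** In Number of subjects, state that 24.3% to 35.7% assumes no within-centre correlation, and add the half-width for one plausible ICC once the number of centres is known.

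In Data analysis method:

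- Report the 95% interval of the overall severe-toxicity rate with a variance that accounts for centre, using a small-sample correction and pooling very small centres by a rule fixed in advance.
- Repeat the logistic models accounting for centre, by random intercept or cluster-robust variance, as a prespecified sensitivity analysis. Say which factors change materially.

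The cost is wording and a few lines of analysis, with no new patients or data. The downsides are a slightly wider interval, an imprecise centre variance if centres are few, and centre-conditional odds ratios if a random intercept is chosen. If the correlation turns out to be near zero, the results will barely change.
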